3.3 Ineligibility Criteria

1. Patients receiving any other investigational agents are ineligible.
2. Patients must not have received prior anti-VEGF therapy including bevacizumab (i.e. patients must be bevacizumab naïve)
3. Patients with a history of allergic reactions attributed to compounds of similar chemical or biologic composition to PT2385 are ineligible.
4. Patients on enzyme-inducing anti-epileptic drugs (EIAED) are not eligible for treatment on this protocol. Patients may be on non-enzyme inducing anti-epileptic drugs or not be taking any anti-epileptic drugs. Patients previously treated with EIAED may be enrolled if they have been off the EIAED for 10 days or more prior to the first dose of PT2385.
5. Patients with a history of bleeding diathesis are ineligible.
6. Patients who have not recovered to $<$ CTCAE grade 2 toxicities related to prior therapy are ineligible.

7. Patients with uncontrolled intercurrent illness including, but not limited to, ongoing or active infection, symptomatic congestive heart failure, clinically significant cardiac disease, unstable angina pectoris, cardiac arrhythmia, or psychiatric illness/social situations that would limit compliance with study requirements, are ineligible.
8. Pregnant women are excluded from this study because the effects of PT2385 on a fetus are unknown. Because there is an unknown but potential risk for adverse events in nursing infants secondary to treatment of the mother with PT2385, breastfeeding should be discontinued if the mother is treated with PT2385.
9. HIV-positive patients on combination antiretroviral therapy are ineligible due to potential drug-drug interactions with PT2385.

[figure not shown]
4.0 TREATMENT PLAN

This is a Phase II, open-label, multicenter efficacy study of PT2385 as monotherapy in patients with recurrent glioblastoma. All subjects must have had histological confirmation of glioblastoma by either biopsy or resection that is progressive or recurrent following radiation therapy + temozolomide.

4.1 Treatment Schema

The goal of this study is to estimate the efficacy of PT2385 as measured by radiographic response in recurrent GBM.

Following enrollment, patients will receive PT2385 at the recommended phase II dose of 800 mg twice daily, continuously in 28-day cycles until progression or unacceptable toxicity. Patients will be followed by routine blood work, and general and neurological examination. A brain MRI will be performed prior to every odd-numbered cycle (every 8 weeks). Response will be assessed by RANO criteria (Section [8.1](#)).

Blood samples to characterize the plasma pharmacokinetics and pharmacodynamics of PT2385 will be obtained from all patients at baseline and in Weeks 1, 2, and 4 of the first

cycle (see Sections [9.5.1](#) and [9.5.2](#)). A blood sample for pharmacogenomic assessment will also be obtained at baseline (Section [9.5.3](#)).

Patients at qualified sites will have simultaneous pH- and hypoxia-weighted MRI performed at baseline (Section [9.5.4](#)).

Patients will continue receiving PT2385 until they meet the criteria for disease progression or other criteria for going off treatment (Section [10.0](#)). Standard of care treatment options will exist for patients who suffer tumor progression or recurrence on treatment. All patients will be followed for progression-free and overall survival. Overall survival will be assessed as the date from treatment start to death from any cause.

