4.2 Treatment Requirements

All eligible patients who consent to this study must have a baseline (post-operative, if surgery is applicable) pre-treatment MRI showing measurable disease (i.e. 1 cm x 1 cm enhancement). This baseline scan must be done within 21 days prior to the initiation of treatment.

Prior to every cycle patients must have:

1) ANC \geq 1500/ μ l and platelets \geq 100,000 / μ l.

AND

2) All toxicities recovered to \leq grade 1 (or tolerable grade 2 for non-hematologic toxicity) or \leq baseline.

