5.0 DOSING DELAYS/DOSE MODIFICATION FOR TOXICITY

Clinically significant adverse events or abnormal laboratory values assessed as unrelated to disease progression, intercurrent illness, or concomitant medications may require dose delay and/or dose modification. Such toxicities must have an attribution of possible, probable, or definite to PT2385 (see Section [9.2.2](#)). If multiple toxicities occur, dose modification decisions should be based on the most severe toxicity.

For patients experiencing toxicity meeting the criteria below, PT2385 will be stopped. If the patient recovers (\leq grade 1 [or tolerable grade 2 for non-hematologic toxicity] or \leq baseline) a dose reduction is required for subsequent doses. Skipped doses will not be made up. If there is any question or clarification required concerning a toxicity, the treating site should contact the ABTC Central Office to determine patient's toxicity status. The ABTC Central Office, with the Study Chair (who may consult with Peloton Medical), will make the final decision.

- Hematological toxicities will require dose modification if any of the following occur and complete blood counts and differentials were obtained according to the

mandated schedule (CBC, differential, and platelets drawn twice a week until the ANC \geq 1500/ mcL and platelets \geq 100,000/ mcL): grade 3 or 4 lymphopenia will not be considered a toxicity requiring dose modification.

- ANC of $<$ 500/ mcL
- Platelets $<$ 25,000/ mcL
- Febrile neutropenia
- Any hematological toxicity that prevents administration of \geq 80% of the planned PT2385 doses for that cycle

➤ Non-hematological toxicities will require dose modification if any of the following occur:

- Grades 3-4 severity (except nausea, vomiting, and diarrhea without sufficient prophylaxis; except alopecia; except grade 3 hyperglycemia; except grade 3 electrolyte disturbances that are asymptomatic and that respond to replacement therapy; and except grade 3 neurologic toxicity responding within two weeks to steroids, anticonvulsants, or electrolyte correction; and except Grade 3 asymptomatic hypoxia. A subject's first episode of deep venous thrombosis [DVT] or pulmonary embolism [PE] will not require dose modification)

ANY TREATMENT RELATED TOXICITY (AS DEFINED ABOVE) CAUSING DELAY IN TREATMENT OF OVER 21 DAYS IN THE START OF A CYCLE WOULD RESULT IN TAKING THE PATIENT OFF TREATMENT.

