8.0 RESPONSE ASSESSMENT / SAFETY AND QUALITY ASSURANCE

8.1 Criteria for Response Assessment

Subjects with measurable disease will be assessed by the RANO (radiographic assessment in neuro-oncology) criteria (Wen et al., 2010). For the purposes of this study, subjects should be re-evaluated at the end of every 2 cycles (approximately every 8 weeks) with a contrast-enhanced cranial MRI scan. The response will be determined as outlined in the RANO criteria below.

Measurable disease. Bidimensionally, contrast-enhancing, measurable lesions with clearly defined margins by MRI scan, with a minimal size of 1 cm x 1 cm, and visible on 2 axial slices which are at least 5 mm apart with 0 mm skip. Measurement of tumor around a cyst or surgical cavity, if necessary, requires a minimum thickness of 3 mm. If there are >2 lesions (multifocal) at baseline, the investigator must choose the largest two to be followed before a participant is entered on study. The remaining lesions will be considered nonmeasurable for the purpose of objective response determination. Unless progression is observed, objective response can only be determined when all measurable and nonmeasurable lesions are assessed.

Complete Response – CR (requires *all* of the following):

- a) Complete disappearance of all enhancing measurable and non-measurable disease sustained for at least 4 weeks. In the absence of a confirming scan 4 weeks later, this scan will be considered only stable disease.
- b) No new lesions.
- c) All measurable and non-measurable lesions must be assessed using the same techniques as baseline.
- d) Subjects must be off corticosteroids (or on physiologic replacement doses only).
- e) Stable or improved non-enhancing (T2/FLAIR) lesions.
- f) Stable or improved clinically.

Note: Subjects with non-measurable disease cannot have a complete response. The best response possible is stable disease.

Partial Response – PR (requires *all* of the following):

- a) Greater than or equal to 50% decrease compared to baseline in the sum of products of perpendicular diameters of all measurable enhancing lesions sustained for at least 4 weeks. In the absence of a confirming scan 4 weeks later, this scan will be considered only stable disease.
- b) No progression of non-measurable disease.
- c) No new lesions.
- d) All measurable and non-measurable lesions must be assessed using the same techniques as baseline.

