8.2 Assessment of Response

Assessment of response will begin with the MRI performed just prior to *every oddnumbered* treatment cycle. If during any scheduled MRI, the subject has a Complete Response or Partial Response, the MRI should be repeated prior to the next cycle. All scans are to be compared to the smallest measurement scan to date. The subject will then return to the every odd-numbered cycle schedule. This is required to confirm the duration of response. Subjects will be classified as responders if they have a minimum duration of response for 4 weeks at any time after the first cycle of PT2385. MRI scans of subjects showing tumor response will be centrally reviewed by a neuroradiologist who will independently assess tumor size and compute percent tumor regression.

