9.0 MONITORING OF PATIENTS

9.1 Table of Required Observations

PT2385 (28-Day Cycles)

	Baseline	Days 1-28 of every cycle	Cycle 1	Weekly During Cycle 1	Weekly During All Cycles	Pre-Odd Cycles (cycles 3+)	Pre-Even Cycles	Off Treatment	30 Days post-last dose
PT2385		6							
Glucocorticoids Dose Evaluation	1					5		8	
AE Evaluation	1			7		5	5	8,10	11
MRI	1,15					5		8	
H&P/Neuro Exam	1					5	5	8	
KPS	1					5	5	8	
Vital Signs with pulse oximetry	1,2			2,7		2,5	2,5	2,8	
CBC, Diff, Platelets	1				9,7	5,9	5,9	8	
Serum Chemistry	1,3			3,7		3,5	3,5	3,8	
APTT or PTT	1								
Serum Pregnancy Test	1,4								

Plasma Samples for Pharmacokinetics			12						
Plasma Samples for Pharmacodynamics			13						
Plasma Sample for Pharmacogenomics	14								
Archived Tumor Tissue	16								

- 1– All baseline measurements must be done within minus 21 calendar days of treatment administration unless otherwise specified.
- 2– Including blood pressure, respiratory rate, heart rate, temperature, weight, height: height is required at baseline only; weight is required at pre-odd cycle evaluations only. Patients with dyspnea or asymptomatic desaturation (oxygen saturation <92%), will be further evaluated as clinically indicated: evaluation may include chest x-ray, arterial blood gas analysis, pulmonary function testing including diffusion capacity, co-oximetry, as well as evaluation for specific causes of hypoxia/dyspnea.
- 3– Including albumin, alkaline phosphatase, total bilirubin, calcium, creatinine, magnesium, phosphorus, potassium, SGOT, SGPT, sodium.
- 4– For women of child-bearing potential.
- 5– Within minus 5 calendar days of cycle start.
- 6– PT2385 is administered orally twice daily on Days 1-28 of each 28-day cycle (see Section [4.3.1](#)). Patients are required to keep a medication diary. 7– ± 1 day
- 8– Evaluations done within +7 days of off treatment date unless indicated: do not repeat: if MRI within minus 14 days of off-treatment date; if H&P/neuro, KPS, labs within minus 5 days of off-treatment date.
- 9– If ANC < 1500 or plts < 100,000, CBCs/differentials will be repeated twice a week until counts are recovered (ANC ≥1500 or plts ≥100,000) per protocol. If counts are recovered (ANC ≥1500 or plts ≥100,000) on day of scheduled drawing do not repeat until next protocol schedule day
- 10 – Adverse Events must be followed for at least 30 days from last dose of PT2385.
- 11– Perform within +14 days of the 30-day post-last dose date.

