10.1 Off Treatment Criteria

1. **Disease Progression:** Remove patient from protocol therapy at the time progressive disease is documented. Disease progression is defined as: Progressive neurologic abnormalities not explained by causes unrelated to tumor progression (e.g. anticonvulsant or corticosteroid toxicity, electrolyte abnormalities, hyperglycemia, etc.) or a greater than 25% increase in the measurement of the tumor by MRI scan. If neurologic status deteriorates, on a stable or increasing dose of steroids, or if new lesions appear on serial MRI, further study treatment will be discontinued.
2. **Adverse Event:**
 - Intercurrent illness that prevents further administration of treatment
 - Patients who experience unacceptable toxicity. Patients removed from study for unacceptable adverse events will be followed until resolution or stabilization of the adverse event.
3. **Patient Withdrawal:** Patient's refusal to continue treatment: in this event, document the reason for withdrawal.

4. **Non-Compliance:** Failure to comply with protocol (as judged by the investigator such as compliance below 80%, failure to maintain appointments, etc.)
5. **Physician Decision:** If at any time the treating physician feels constraints of this protocol are detrimental to the patient's health remove the patient from protocol therapy.
6. **Protocol Defined Delay:**
 - Patients who experience a treatment-related toxicity causing a delay in treatment >21 days
 - Delay in protocol >28 days for major events or other non-treatment related delays
 - Patients who require >2 dose reductions
 - Patients who must be put on an enzyme-inducing anti-epileptic drug (EIAED) during the study
7. **Death**

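### Response MRIs follow odd-numbered cycle starts, so the stated 8-week interval becomes 11–12 weeks after one maximally delayed start and recorded PFS is, on average, biased upward

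*Combined protocol and SAP*

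**What the plan says.** All on-treatment response scans are timed by cycle:

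- Section 4.1: treatment runs "continuously in 28-day cycles until progression or unacceptable toxicity", and "A brain MRI will be performed prior to every odd-numbered cycle (every 8 weeks".
- Section 8.1: "subjects should be re-evaluated at the end of every 2 cycles (approximately every 8 weeks) with a contrast-enhanced cranial MRI scan".
- Section 8.2: "Assessment of response will begin with the MRI performed just prior to" each odd-numbered cycle. A scan showing response is to be repeated before the following cycle.
- Table 9.1, footnote 5, which governs the MRI in the pre-odd-cycle column: "Within minus 5 calendar days of cycle start".

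Cycle starts can move:

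- Section 4.2: "Prior to every cycle patients must have" adequate counts and recovered toxicities.
- Section 5.0 takes a patient off treatment for treatment-related toxicity "CAUSING DELAY IN TREATMENT OF OVER 21 DAYS IN THE START OF A CYCLE". Section 5.1 sets the same 21-day limit on a hold.
- Section 10.1 lists as an off-treatment reason "Delay in protocol >28 days for major events or other non-treatment related delays". Section 5.2 also gives 28 days for major events.

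Section 5.0 adds that doses skipped during a hold are not made up. Section 11 measures PFS from treatment start to the date progression was declared. It has rules for missing scans and for deaths, but no interval-censored or scheduled-date analysis.

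**The concern.** The cycle-based schedule and the 8-week figure agree only if no cycle starts late. When Cycle 3 is delayed, a site must either give up the 8-week interval or scan outside the 5-day window before the cycle. Following the window makes the scan late. Radiographic progression is dated by the scan that shows it, so a patient with a delayed cycle tends to have progression dated later because of the delay.

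Delay depends partly on toxicity, so this error is not random. The Section 11 rules for missing scans would probably not catch it: the section does not define a planned scan, and a scan that moves with its cycle is not obviously missing. At stake is the accuracy of the PFS estimate and, to a lesser degree, when response is first seen and confirmed.

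**Working it through.** **1. The plan's own figure.** Cycle length is 28 days (Section 4.1). Two cycles: 2 × 28 = 56 days = 8 weeks. This reproduces the stated interval when no start is delayed.

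**2. Interval with delayed starts.** Interval = 56 + delay of the even-cycle start + delay of the odd-cycle start.

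| Delays (days) | Interval |
|---|---|
| one of 21 | 77 days = 11 weeks |
| one of 28 | 84 days = 12 weeks |
| 21 + 21 | 98 days = 14 weeks |
| 21 + 28 | 105 days = 15 weeks |
| 28 + 28 | 112 days = 16 weeks |

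The last three rows need both starts in the pair delayed to the limit. They also assume that the limit applies afresh to each delay, which the text does not say outright.

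**3. Effect on recorded PFS in a delayed patient.** Assumptions, none from the documents: exponential progression times with true median *m* of 6–16 weeks, detection at scans only, and the first scan moved from week 8 to week *L* with later scans every 8 weeks. (The 10–15% six-month PFS that Section 2.1 gives for salvage chemotherapy implies, if exponential, a median of 182.6 × ln 2 / −ln 0.10 = 55 days to 182.6 × ln 2 / −ln 0.15 = 67 days, which is inside this range.)

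With *L* = 11, a progression in weeks 0–8 is recorded at 11 instead of 8 (3 weeks later). One in weeks 8–11 is recorded at 11 instead of 16 (5 weeks earlier). The pattern then repeats. Let S(t) = 2^(−t/m). For *L* between 8 and 16 weeks, the share recorded earlier is q = [S(8) − S(L)] / [1 − S(8)], and the mean shift is (L − 8) − 8q.

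- *L* = 11, *m* = 6: S(8) = 0.397, S(11) = 0.281, q = 0.19; shift = 3 − 1.54 = 1.46 weeks.
- *L* = 11, *m* = 16: S(8) = 0.707, S(11) = 0.621, q = 0.29; shift = 3 − 2.35 = 0.65 weeks.
- *L* = 12, *m* = 6: S(12) = 0.250, q = 0.24; shift = 4 − 1.95 = 2.05 weeks.
- *L* = 12, *m* = 16: S(12) = 0.595, q = 0.38; shift = 4 − 3.07 = 0.93 weeks.

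So with an 11-week first scan, 71–81% of delayed patients are recorded later and 19–29% earlier. At the 16-week extreme the mean shift is 2.3–4.8 weeks and nobody is recorded earlier. A simulation of 2,000,000 progression times per case gave the same values.

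**4. Effect on the whole cohort.** The documents give no frequency of delayed starts. If 10–30% of patients are delayed, mean PFS moves by 0.10 × 0.65 = 0.07 to 0.30 × 1.46 = 0.44 weeks for *L* = 11. At the 16-week extreme it moves by 0.2–1.5 weeks. The Kaplan–Meier median either stays put or jumps to the delayed scan date. With *m* = 6 and *L* = 11 it stays at 8 weeks if 10% are delayed and moves to 11 weeks if 20% are. With *m* = 12 it stays at 16 weeks throughout.

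**5. Confirmation scan.** It is tied to the next cycle, nominally 28 days later. A maximal delay of that cycle puts it at 28 + 21 = 49 days or 28 + 28 = 56 days.

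**The case against.** Several points on the other side stand.

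- A reader might infer that every hold postpones the scan. It does not: skipped doses are not made up, so a hold contained within a cycle need not move the next start.
- Section 8.1 times the scan at the end of two cycles. On that reading a late odd-cycle start does not move the scan, and only a late even-cycle start does. A scan may also be done within its window before the delay is declared. But a scan done on time ahead of a Cycle 3 that starts 21 days late would breach the 5-day window in Table 9.1, so the wordings conflict.
- Progression can be found off schedule. Clinical deterioration counts as progression (Section 8.1), examination and performance status precede every cycle after the first and an off-treatment MRI is listed (Table 9.1), repeat imaging is recommended on suspected deterioration (Section 4.4), and deaths can count as events (Section 11). The shifts above are therefore upper-end illustrations for their assumptions.
- Delays may be uncommon. Section 9.2.1 reports no dose-limiting toxicity in dose escalation, no discontinuation for adverse events in Part 1 of the first-in-human study, and mostly Grade 1–2 events there.
- PFS is secondary and only estimated, in one arm, with no external comparison planned.

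A reader might also divide a maximal delay by the 55–67 day median (21/67 = 31%, 28/55 = 51%) and call the result the PFS bias. That ratio compares a worst-case scan shift with an assumed median; the average bias is smaller, as step 3 shows.

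Finally, moving only the 8-week scan to the calendar could harm confirmation of response. If Cycle 2 starts at day 49 and Cycle 3 at day 77, a day-56 scan would be confirmed on days 72–77, only 16–21 days later, and Section 8.1 requires 4 weeks. This argues for a fuller fix, not for leaving the schedule as it is.

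**Conclusion.** The point holds as a low-cost improvement. The stated 8-week interval becomes 11–12 weeks after one maximally delayed cycle start; 14–16 weeks is an extreme. Recorded PFS is biased upward on average in patients with delayed starts. That some of them are recorded earlier rules out the stronger reading that PFS is lengthened in each such patient. The size rests on the assumed exponential model, scan-only detection and an unknown delay frequency: about 0.7–2.1 weeks on average per delayed patient for one maximal delay, and well under a week in the cohort mean if 10–30% are delayed.

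A reader might infer that the two-stage decision is compromised. The documents do not support that: Section 11 counts responses at any time during treatment, with no fixed assessment date. Delay affects only when response is seen and confirmed. A late confirmation scan could miss a response that has since been lost, but nothing in the documents shows how often.

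**What to change.** - In Sections 4.1, 8.1 and 8.2 and Table 9.1, schedule on-treatment MRI every 56 days from Cycle 1 Day 1, with a fixed window (for example minus 5 to plus 3 days), whether or not a cycle starts late.
- In Section 8.2, time the confirmation MRI at least 4 weeks after the scan that first showed response, instead of by the next cycle.
- Reconcile the end-of-two-cycles wording in Section 8.1 with the 5-day pre-cycle window in Table 9.1, and say that a delayed cycle does not require a repeat scan just to meet that window.
- In Section 11, define a planned scan by this calendar and add a PFS sensitivity analysis that is interval-censored or uses scheduled scan dates.

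The cost is an amendment to the wording and one added analysis. In delayed patients the scan may need a separate visit, and there may be slightly more scans per cycle. No dosing or delay rule changes.

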4.2 Treatment Requirements

All eligible patients who consent to this study must have a baseline (post-operative, if surgery is applicable) pre-treatment MRI showing measurable disease (i.e. 1 cm x 1 cm enhancement). This baseline scan must be done within 21 days prior to the initiation of treatment.

Prior to every cycle patients must have:

1) ANC \geq 1500/ μ l and platelets \geq 100,000 / μ l.

AND

2) All toxicities recovered to \leq grade 1 (or tolerable grade 2 for non-hematologic toxicity) or \leq baseline.

4.3 Drug Administration

No investigational or commercial agents or therapies other than those described below may be administered with the intent to treat the patient's malignancy.

Treatment will be administered on an outpatient basis. Patients will be provided with medication diaries ([Appendix I](#)) and instructed in their use. Patients will be instructed to bring all unused medication and their diaries to each study visit for assessment of compliance.

